24 TERMINATION OF STUDY

Investigators will be notified by Veniti, Inc. of study termination for any reason. Investigators are required to submit all patient and study data in a timely manner and comply with Veniti, Inc.'s request regarding disposition of the outstanding investigational devices.

25 ADDITIONAL RECORDS AND REPORTS

25.1 Investigator Records

Records are subject to FDA inspection and must be retained for a period of two (2) years after the latter of the two dates:

- the date on which the investigation is terminated or completed; or
- the date that the records are no longer required for purposes of supporting an application to the FDA to market the device.
- the investigator is responsible for the preparation (review and signature) and retention of the records cited below.
- All correspondence which pertains to the investigation including required reports
- Device Disposition Record
- Screening Logs
- Subject's case history records, including:
- Signed Informed Consent document
- All relevant patient complaints
- Observations of adverse events
- Medical history
- All case report forms and supporting data
- Documentation of protocol deviations, including date(s) and reason(s) for deviation(s)
- Signed Protocol, Curriculum Vitae and Financial Disclosure (These must be submitted to Veniti and kept on file at the investigative center.)

25.2 Investigator Reports

The investigator is responsible for the preparation (review and/or signature) and submission of the reports cited in Table 25.2.1 as required by 21 CFR 812

STE-HUM-007P US Clinical Protocol Revision C

Subpart G and sponsor. These are also subject to FDA inspection and the retention requirements described above for Investigator Records.

REPORT	SUBMIT TO	DESCRIPTION/CONSTRAINTS
ТО		
Unanticipated	Monitor &	If an unforeseen complication is determined to be an
Adverse Device	IRB/EC	unanticipated adverse device effect, then the investigator's
Effect		report must be submitted within 10 working days after the
		investigator first learns of the effect.
Withdrawal of	Sponsor	The investigator must report a withdrawal of the reviewing
IRB/MEC Approval		IRB/MEC approval within 5 working days.
Progress Report	IRB/EC	The investigator must submit this report if the study lasts
		longer than one year.
Deviation from	Sponsor &	If the deviation may affect the scientific soundness of the
Investigational	IRB/EC	plan or the rights, safety and welfare of the subjects the
Plan		deviation must be approved by Veniti, reviewing IRB/MEC,
		and the FDA. If the deviation does not affect these issues
		(study soundness, rights, safety, etc.) then only Veniti must
		approve it.
Failure to Obtain	Sponsor &	The Investigator must make notification within 5 working
Informed Consent	IRB/EC	days after device use. The report must include a brief
		description of the circumstances justifying the failure to
		obtain informed consent and include written concurrence
		by a licensed physician not involved in the investigation.
Final Report	Sponsor &	This report must be submitted within three months after
	IRB/MEC	termination or completion of the investigation.

Table 25.2.1: Investigator Reports

Veniti Records

Veniti will maintain the following records and submit reports per Table 25.2.2:

- 1 All vital correspondence that pertains to the investigation including reports
- 2 Device Shipment/Disposition Record
- 3 Signed Protocol Cover Pages, Investigator Agreements Curriculum Vitae
- 4 IRB/EC Approval Letter
- 5 Adverse events and complaints
- 6 Case Report Forms
- 7 Clinical Investigation Plan
- 8 Monitoring Reports

Table 25.2.2: Venit	li Reports	
REPORT	SUBMIT TO	DESCRIPTION
Unanticipated	FDA, all IRBs/MECs	Veniti will report on any and all unanticipated
Device Related	and all Investigators	device-related adverse event evaluation within 10
Adverse Event		working days.
Withdrawal of	FDA, all IRBs/MECs	Notification will be made within 5 working days.
IRB/MEC	and all Investigators	
Approval		
Withdrawal of	All IRBs/MECs and all	Notification will be made within 5 working days.
FDA Approval	Investigators	
Current	FDA	Veniti will submit a list of names and addresses of
Investigator List		all participating investigators at 6 month intervals.
Progress Report	FDA, all IRBs/MECs	A progress report will be submitted at least yearly.
	and all Investigators	
Recall and	FDA, all IRBs/MECs	Notification will be made within 30 working days
Disposition	and all Investigators	and will include the reasons for any request that an
		investigator return, repair or otherwise dispose of
		any devices.
Final Report	FDA, all IRBs/MECs	Veniti will notify FDA within 30 working days of the
	and all Investigators	completion or termination of the investigation. A
		final report will be submitted within 6 months after
		completion or termination.
Failure to Obtain	FDA/IRB/	A copy of the investigator's report will be submitted
Informed Consent	MEC	within 5 working days of notification.

Table 25.2.2: Veniti Reports

25.3 IRB/EC Records

Each reviewing IRB/MEC must maintain the following records relating to the investigation:

- Records of protocols and continuing review
- All pertinent correspondence between IRB and Investigator
- Statement of significant new finding provided to subjects
- All records of membership and affiliation
- Meeting minutes

26 APPENDIX 1: VENOUS ANATOMY DESIGNATIONS

- Supra-renal inferior vena cava
- Infra-renal inferior vena cava
- Left common iliac vein
- Left external iliac vein
- Left common femoral vein
- Left femoral vein
- Right common iliac vein
- Right external iliac vein
- Right common femoral vein
- Right femoral vein

STE-HUM-007P US Clinical Protocol Revision C

Confidential

Page 55 of 70

27 APPENDIX 2: EXTENDED ANTICOAGULATION PROTOCOL

VENITI

28 APPENDIX 3: FRACTURES

Assessment of the venous stents will be performed at 12 months, and at any interval evaluation, for analysis of strut fracture. High-resolution digital images should be obtained in a diagnostic X-Ray unit, or in an angiography suite (if performed as part of an interval evaluation). All images will be submitted to the Core Laboratory for assessment of strut fracture.

Fractures will be assessed as per Jaff, et al.⁶ Data to be collected for each fracture identified includes:

- Limb (right or left)
- Venous segment(s) where fractures are located
- Overlapping versus non-overlapping
- Type of fracture (Type I, II, III, IV)

STE-HUM-007P US Clinical Protocol Revision C

29 APPENDIX 4: ADDITIONAL STUDY DEFINITIONS

Allergic Reaction: A physical reaction to a substance that can cause wheezing, edema (swelling), induced thrombotic events, uticaria (rash), and/or shock.

Arterio-venous (AV) Fistula: A communication between an artery and a vein in which the arterial blood flows directly into a neighboring vein.

Bleeding: Blood loss resulting from the percutaneous interventional procedure or adjunctive drug therapy that may require transfusion of blood products.

Catheter-Directed pharmacologic thrombolysis: An image guided technique involving infusion of thrombolytic agents through a multi-side hole infusion catheter or wire placed directly into a venous thrombus through a remote puncture site.

CEAP Classification: A method for evaluating venous disease of the leg based on clinical, etiologic, anatomic, and pathophysiologic data.

Class 0	No visible or palpable signs of venous disease (only symptoms)
Class 1	Telangiectasias or reticular veins
Class 2	Varicose veins
Class 3	Oedema
Class 4	Skin changes ascribed to venous disease (e.g. pigmentation, venous eczema, lipo-dermatosclerosis)
Class 5	Skin changes as defined above with healed ulceration
Class 6	Skin changes as defined above with active ulceration

Table 29.1: CEAP Classification of CVI

Central: closer to the heart; antegrade to the flow

CIVIQ-2 (Chronic Venous Insufficiency Questionnaire): A self-administered questionnaire which explores four dimensions related to chronic lower limb venous insufficiency. The four dimensions are psychological, physical and social functioning and pain.¹⁵

Death: The termination of life.

Diabetes (History of): Defined as patients who have been diagnosed with either Type I or Type II diabetes and are currently taking oral hypoglycemics or insulin or have a hemoglobin A1C > 7%.

Discharge: The time point when the subject is released from the admitting hospital, transferred to another facility, or has expired.

Femoropopliteal DVT: A DVT involving the femoral or popliteal venous segments, or both without extension to the common femoral or iliac veins.

Fever: An increase in internal body temperature to levels that are above normal (37°C, 98.6°F).

STE-HUM-007P US Clinical Protocol Revision C

Confidential

Page 58 of 70

Gastrointestinal (GI) bleeding: any bleeding that starts in the gastrointestinal tract, which may extend from the mouth to the anus.

Hematoma: Localized mass of extravasated blood \geq 5 cm that prolongs hospitalization.

Hemorrhage: Bleeding requiring hospitalization, repeat procedure, operation or transfusion.

Hypertension: Increase in systolic blood pressure above 140 mm Hg or a diastolic blood pressure above 90 mm Hg.

Hypotension: Fall in systolic blood pressure that requires intravenous treatment with vasopressors or inotropic agents.

lliofemoral DVT: DVT involving complete or partial thrombosis of the iliac vein or the common femoral vein, or both, with or without femoropopliteal DVT.

Index Procedure: The procedure in which the subject has the study procedure performed or attempted.

Infection: Inflammation caused by bacterial or viral sources, such as, urinary tract infection, puncture site infection, sepsis, endocarditis, and bacteremia from IV site.

Inflammation: An immunologic response to infection or trauma that can result in localized redness, swelling, heat, pain and dysfunction of the organs involved.

Invasive Assessment/Procedure: Any assessment, intervention or therapy that penetrates the skin, excluding administration of parenteral fluids or drugs.

Kidney Failure: Failure of the kidneys to perform essential functions that requires dialysis.

Myocardial Infarction (Non-Q wave): Post-treatment elevation of CK-MB more than 3 times the upper limit of lab normal value without evidence of pathologic Q-waves present on EKG. Elevated serum troponin levels are not sufficiently validated to be considered sole evidence of an MI in the absence of CK-MB elevations.

Myocardial Infarction (Q wave): Development/appearance of new pathological Q-waves in more than 2 contiguous leads per 12-lead electrocardiogram (EKG/ECG).

Peripheral: refers to a location away from the heart; retrograde to the flow

Physician-Directed Subject Withdrawal: Withdrawal of a subject from the study at the direction of the Principal Investigator. Reasons for physician-directed subject withdrawal include, but are not exclusive to: the subject is not adhering to the Study Protocol requirements, the subject has enrolled in another study that conflicts with the VIRTUS outcomes of interest, or the physician deems it in the best interest for the safety or welfare of the subject to withdraw.

Principal Investigator: Physician responsible for overall clinical management of subjects enrolled at his/her institution. Assumes overall responsibility and accountability for the clinical team and for data obtained from each subject participating in the study. Ensures compliance with the Study Protocol, applicable laws, and applicable regulations; ensures

STE-HUM-007P US Clinical Protocol Revision C

Confidential

Page 59 of 70

informed consents are signed, and reviews and signs eCRF indicating documents are accurate and complete.

Protocol Deviation: Any divergence from the Study Protocol.

Pseudoaneurysm: Perforation of the vessel with arterial blood flow outside of the vessel.

Sepsis: Systemic inflammatory response to infection.

Serious Adverse Device Effects: Any adverse device effects that result in any consequences characteristic of a serious adverse event or might have led to any of these consequences if suitable action had not been taken or intervention had not been made or if circumstances had been less opportune.

Serious Adverse Event: Any adverse events that led to a death or led to a serious deterioration in the health of the subject that 1) resulted in a life-threatening illness or injury, 2) resulted in a permanent impairment of a body structure or a body function, 3) required inpatient hospitalization or prolongation of existing hospitalization, or 4) resulted in medical or surgical intervention to prevent permanent impairment to a body structure or body function. This definition also includes any adverse event that led to fetal distress, fetal death or a congenital abnormality or birth defect.

Stroke: Neurological dysfunction caused by a brain disturbance or ischemia, with clinical symptoms lasting >24 hours or imaging of an acute clinically relevant brain lesion in patients with rapidly vanishing symptoms.

Study Coordinator: Employee at study site who assists Principal Investigator with study activities as delegated by the Principal Investigator, including tracking subjects involved in the study, scheduling testing and follow-up visits, maintaining study records, completing and providing eCRFs to the Sponsor in a timely manner.

Sub-Investigator(s): Physician(s) responsible for study activities in coordination with Principal Investigator and in accordance to the Study Protocol.

Systemic Infection: the bloodstream infection that affects a number of organs and/or tissues, or affects the body as a whole.

Transient Ischemic Attack (TIA): Brief episode of neurological dysfunction caused by a focal disturbance of brain or retinal ischemia, with clinical symptoms typically lasting less than 1 hour, and without evidence of infarction.

Vascular Complications: Adverse sequelae within the vasculature which can result from catheter-based interventions, including arterio-venous fistula, bleeding, hematoma, infection and pseudoaneurysm (see Access Site Complications), aneurysm, venous perforation, venous rupture, venous spasm, hemorrhage, hypertension, hypotension, sub-acute closure, and thrombosis.

Venous Clinical Severity Score (VCSS): An objective means to clinically assess venous disease¹⁶. (See Appendix 7.)

Visual Analog Scale (VAS): A scale for patients to report their pain level during activity or movement. (See Appendix 6.)

STE-HUM-007P US Clinical Protocol Revision C

Confidential

Page 60 of 70

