9.6 Discharge or Three Days Post-Procedure (whichever comes first)

- Duplex ultrasound to determine post-procedural target vessel lumen diameter (For patients refusing the venographic assessment at 12 months [or prior Interval Evaluation, as applicable], DUS-determined patency will be used instead, with the DUS obtained at the Discharge or Three Days Post-Procedure visit serving as the baseline).
- Determination of discharge
- Anticoagulation Review, based on the Extended Anticoagulation Protocol (See Appendix 2.)
- Adverse event assessment
- Patients who do not meet intra-procedural inclusion criteria (and who do not receive the implanted study device) should be followed only through hospital discharge for protocol deviations and adverse events. This visit will conclude participation for these screen failed patients. These subjects will not be included in the statistical analysis.

9.7 1 Month Evaluation (30 days -7/+14 days)

- Physical examination (to assess for the presence of Adverse Events)
- Anticoagulation Review, based on the Extended Anticoagulation Protocol (See Appendix 2.)

9.8 6 Month Evaluation (180 days ± 30 days)

- Physical examination (to assess for the presence of Adverse Events)
- Duplex ultrasound (required only for first 30 patients to assess patency)
- CIVIQ-2 Quality of Life questionnaire (See Appendix 5.)
- VAS pain score
- VCSS (See Appendix 7.)
- Anticoagulation Review, based on the Extended Anticoagulation Protocol (See Appendix 2.)

9.9 12 Month Evaluation (365 days ± 60 days)

Patients that refuse the venogram and IVUS at this visit should have all other assessments listed here performed:

- Physical examination (to assess for the presence of Adverse Events)
- Assessment of primary patency by venography

STE-HUM-007P US Clinical Protocol Revision C

- Determination of residual external venous segment compression, stent recoil, and lesion coverage by IVUS
- Duplex ultrasound for all patients (For patients refusing the venographic assessment at this visit, DUS-determined patency will be used towards the primary efficacy endpoint instead.)
- Assessment of stent integrity by bi-plane X-Ray (See Appendix 3.)
- CIVIQ-2 Quality of Life questionnaire (See Appendix 5.)
- VAS pain score (See Appendix 6.)
- VCSS (See Appendix 7.)
- Anticoagulation Review, based on the Extended Anticoagulation Protocol (See Appendix 2.)

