15.3 Primary Analysis: Per-protocol

All patient data that is available on subjects who drop out during the course of the study will be included. In the primary analysis of the primary endpoints, we will assume that data are missing at random (i.e., it is not the study treatment that is causing the data to be missing) and ignore missing values in the analyses.

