21 SUBJECTS' CONFIDENTIALITY

Information about study subjects will be kept confidential and managed according to the requirements of the Health Insurance Portability and Accountability Act of 1996 (HIPAA). The HIPAA regulations require a signed subject authorization informing the subject of the following:

- What protected health information (PHI) will be collected from subjects in this study •
- Who will have access to that information
- Who will use or disclose that information
- The rights of a research subject to revoke their authorization for use of their PHI.

STE-HUM-007P US Clinical Protocol Revision C

In the event that a subject revokes authorization to collect or use PHI, the Investigator retains the ability to use all information collected prior to the revocation of subject authorization. For subjects that have revoked authorization to collect or use PHI, attempts should be made to obtain permission to collect at least vital status (i.e., fact whether the subject is alive) at the end of their scheduled study period.

All data used in the analysis and summary of this study will be anonymous. Access to subject files will be limited to authorized personnel involved in the study.

At time of enrollment, subjects will be assigned a trial-specific number identifier. This identifier will be used throughout the course of the study (instead of patient name, hospital ID, etc.) to ensure subjects confidentiality.

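### Investigator-directed withdrawal for non-adherence ends follow-up, and the primary analysis then drops the patient; the plan should keep collecting the patency endpoint after such a withdrawal.

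*Combined protocol and SAP*

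**What the plan says.** **Withdrawal.** Appendix 4 defines physician-directed withdrawal as "Withdrawal of a subject from the study at the direction of the Principal Investigator". It is therefore withdrawal from the study, not only from a procedure or a drug. The wording is open-ended; the reasons it names by way of example include: "the subject is not adhering to the Study Protocol requirements, the subject has enrolled in another study that conflicts with the VIRTUS outcomes of interest". The subject's safety or welfare is the other reason given. No section asks for 12-month imaging or other endpoint data after such a withdrawal.

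**Primary analysis.** Section 15.3 states its assumption about missing endpoint data as follows: "we will assume that data are missing at random (i.e., it is not the study treatment that is causing the data to be missing". It adds that the analysis will "ignore missing values in the analyses". Section 15.8.1 keeps a patient only if a patency failure is known or a 12-month image shows success; all others are left out. Available data on drop-outs are used (15.3), and a failure known before 12 months counts even if the patient has since left (15.7).

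**Sensitivity analyses.** Worst-case (missing counted as failure) and tipping-point analyses are planned as supportive (15.3.1). The success rule in 15.7 is the weighted Z-test plus an observed rate above the goal in each stratum; it does not refer to them. Section 15.2 promises a list of non-completers with reasons.

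**The concern.** This is a single-arm, open-label trial against fixed goals, so any selective loss of likely failures raises the observed rate with no control arm to offset it. Ignoring missing values in the weighted test is safe only if, within each of the non-thrombotic (NT) and post-thrombotic (PT) strata, the dropped patients have the same patency as those retained. The reason given in 15.3 is that the device is not causing the loss. That is not enough when the loss follows an investigator's decision about a behaviour that may itself be prognostic. The antithrombotic guidelines in 9.5.3 run through the 12-month visit, and thrombotic occlusion is a component of the primary endpoint, so stopping that therapy could plausibly mark patients at higher risk.

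At stake is the 12-month patency result that supports the marketing application, and in particular the false-success rate of a test set at one-sided 2.5%.

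**Working it through.** **1. Can a failure go unseen?** The 6-month duplex is required only for the first 30 patients (9.8; Section 10, note e), and the 30 feasibility patients are not in the pivotal population (8.1). Interval imaging is triggered by symptoms (9.10). A pivotal patient therefore has no scheduled patency imaging between the discharge duplex and month 12. A patient withdrawn at, say, month 4 with a silent occlusion has no failure event and no 12-month image, and is left out.

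**2. Inputs.** Goals: PT 0.679, NT 0.855. Design rates: 0.779 and 0.955. Weights: 0.74 and 0.26 (15.7). Enrolled: 125 PT and 45 NT (15.1). Evaluable: 156, leaving 170 − 156 = 14 (8.2%) for losses from all causes. Assumed split of the 156: 115 PT and 41 NT.

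**3. The plan's own power.**
- Null standard error = √(0.26² × 0.855 × 0.145/41 + 0.74² × 0.679 × 0.321/115) = 0.0352.
- Critical excess = 1.96 × 0.0352 = 0.069.
- Expected excess = 0.26 × 0.10 + 0.74 × 0.10 = 0.100, so the expected margin is 0.031 (3.1 weighted points).
- Standard error at the design rates = 0.0298; power = Φ(0.0309/0.0298) = Φ(1.036) = 85.0%. Exact enumeration of the two binomials gives 86.9%.

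The target of at least 85% is reproduced. Section 15.7 also states 84%; this point does not depend on the difference.

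**4. False success when the true rates equal the goals.** Drop d patients per stratum whose patency is g points below the goal. The retained rate is (N × goal − d × (goal − g))/(N − d). For 10 PT dropped with g = 0.20: (125 × 0.679 − 10 × 0.479)/115 = 0.696. The probability that the Z-test succeeds, by exact enumeration:

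| Dropped (NT/PT) | g = 0 (at random) | g = 10 | g = 20 | g = 30 |
|---|---|---|---|---|
| 5 (1/4) | 2.6% | 3.2% | 3.9% | 4.7% |
| 14 (4/10) | 2.7% | 4.7% | 7.7% | 12.1% |

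The upward shift in the weighted rate is 0.3, 0.6 and 0.9 points for 5 dropped, and 0.9, 1.8 and 2.7 points for 14. Adding the two observed-rate conditions lowers the probabilities a little (14 dropped, g = 20: 6.6%).

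**5. Overstatement when the retained PT patients have 77.9% patency.** If k of 125 PT patients are withdrawn with true patency p, the weighted overstatement is 0.74 × k × (0.779 − p)/125. The factor 0.74 is needed to compare it with the 3.1-point weighted margin.

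| k | p = 30% | p = 50% | p = 60% |
|---|---|---|---|
| 5 | 1.4 | 0.8 | 0.5 |
| 10 | 2.8 | 1.7 | 1.1 |
| 14 | 4.0 | 2.3 | 1.5 |

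Only one of the nine cells exceeds 3.1. It needs all 14 losses to be PT, all physician-directed, and at 30% patency.

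**6. Can the worst-case analysis replace the data?** With 14 missing and design rates in the other 156, counting the missing as failures gives expected rates of 41 × 0.955/45 = 0.870 and 115 × 0.779/125 = 0.717. The weighted excess is 0.26 × 0.015 + 0.74 × 0.038 = 0.032, against a critical 0.066 at 45/125. That test succeeds 10.5% of the time, so its failure would say little about whether the withdrawals were informative. With all 170 outcomes collected, the exact type I error is 2.4% and power is 88.5%.

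**The case against.** The defence has real force. Appendix 4 is a permissive list, not an instruction to withdraw. Patients with symptoms of obstruction get an interval evaluation whose imaging goes to the core laboratory, and known failures stay in. Non-completers are listed with reasons, and both sensitivity analyses would expose a fragile result. No passage says that non-adherent patients have worse patency, 9.5.3 presents the regimen as guidelines, and no prognostic argument is available for co-enrolment. All of this stands, and it limits the point to patients not known to have failed. It does not supply their outcomes.

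A reader might also infer more than the documents support:
- **A conflict with 9.9.** That section says "Patients that refuse the venogram and IVUS at this visit should have all other assessments listed here performed" and accepts duplex for the endpoint. Declining the venogram is a path the protocol provides for, so there is no contradiction.
- **Section 21 seeking only vital status.** The text is "attempts should be made to obtain permission to collect at least vital status", which is a floor, and it concerns a patient revoking authorization rather than withdrawal by the investigator.
- **Loss of 30-day safety data.** A month-4 withdrawal comes after that endpoint, and 9.10 requires the 30-day assessment whatever the patency status.
- **A contradiction of 15.3.** Loss due to non-adherence is not caused by the stent, so the stated reason is insufficient rather than contradicted.
- **A demonstrated false success.** Even in the extreme cell of step 5, PT patency over all 125 patients is 0.779 − 0.054 = 72.5%, above the 67.9% goal.

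**Conclusion.** The gap is real and cheap to close. The documents allow withdrawal from the study for non-adherence, require no endpoint follow-up afterwards, and then exclude patients without an image or known failure from the test that decides success. For these patients the missing-at-random assumption is not well supported.

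The size is conditional. At the performance goals, the nominal 2.5% test would have a false-success rate of about 3.2% to 4.7% with 5 such losses, and 4.7% to 12.1% if all 14 allowed losses were of this kind. The number of physician-directed withdrawals, their patency and the split by stratum are assumptions, and 14 is the allowance for losses from every cause. The upward direction rests on the inference that non-adherent patients do worse. The documents do not show that investigators would use the rule to remove failing patients.

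**What to change.** In Appendix 4, state that non-adherence, declining a procedure, co-enrolment or any physician-directed withdrawal is recorded (as a protocol deviation where applicable) but does not end endpoint follow-up unless the subject withdraws consent. Deleting the two example reasons would not be enough, because the list is not exhaustive. Leave the safety and welfare ground as it is.

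For anyone who stops visits, seek the 12-month duplex already scheduled for all patients, or permission to collect re-interventions, imaging and SAEs from medical records, with vital status as the last fallback. State in 15.3 and 15.8.1 that all outcomes so obtained enter the primary analysis.

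The cost is protocol wording and some extra site effort to retain or trace these patients. No visit or procedure is added. The consent pages are not in the text reviewed, so whether the consent form also needs a line should be checked.
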